10.5.4 Biomarker Endpoints

The analysis of biomarkers for other exploratory objectives will be described and reported separately.

Phase 1b

- Potential biomarkers which predict and/or are correlated with clinical outcomes to talimogene laherparepvec and pembrolizumab

10.5.5 Sensitivity Analyses

The Bayesian analyses of phase 1b efficacy in [Section 10.5.2.1](#) may be repeated to assess sensitivity due to the choice of prior for pembrolizumab and/or to account for new external results, such as from KEYNOTE-040.

10.6 Safety Analyses

Safety analyses will be conducted separately for phase 1b based on the SAS analysis sets, as follows.

10.6.1 Adverse Events and Disease-Related Events

The Medical Dictionary for Regulatory Activities (MedDRA) version 20.0 or later will be used to code all adverse events (AE) and disease-related events (DRE) to a system

organ class and a preferred term. The CTCAE version 4.0 will be used to grade severity of adverse events. In general, events with missing IP relatedness (AEs only), seriousness, or CTCAE severity grades will be included in the analysis as long as the event is considered treatment-emergent. However, analyses of treatment-related (AEs only), SAE, or grade 3 or higher, or combinations thereof will exclude events with missing relatedness, seriousness, and severity grades, respectively.

The analyses for AEs will include TEAEs unless otherwise specified. The subject incidence of TEAEs will be summarized for all AEs, SAEs, AEs leading to withdrawal of investigational product, grade 3 or **higher** AEs, fatal AEs, talimogene laherparepvec events of interest (EOI), pembrolizumab events of clinical interest (ECI), **and pembrolizumab adverse event of specific interest (AEOSI)**.

Preferred term **and worst grade within each category of EOI (including treatment-emergent EOs and treatment-related EOs), EOI SAEs (including treatment-emergent EOs SAE and treatment-related EOI SAEs), AEOSI (including treatment-emergent AEOSIs and treatment-related AEOSIs) and AEOSI SAE (including treatment-emergent AEOSI SAEs and treatment-related AEOSI SAEs)** will be summarized.

The subject incidence of all TEAEs, SAEs, AEs leading to withdrawal of investigational product, grade 3 or **higher** AEs, and fatal AEs will be tabulated by system organ class, preferred term in descending order of frequency **and worst grade**.

Summaries of **all TEAEs, SAEs, AEs leading to withdrawal of investigational product, grade 3 or higher AEs, fatal AEs, treatment-related AEs**, TEAEs and SAEs occurring in at least 1% of the subjects by preferred term in any treatment arm will be provided in descending order of frequency.

Sensitivity analyses of TEAEs, SAEs, AE leading to withdrawal of investigational product and fatal AEs will be conducted, considering any DRE as an AE.

Subject incidence of DREs, **serious DREs, DREs leading to withdrawal of investigational product** and fatal DREs will be tabulated by system organ class, preferred term, **and worst grade. Summaries of DREs, serious DREs, and DREs leading to withdrawal of investigational product and fatal DREs will be tabulated by preferred term.**

Including all the preferred terms, a comparison of all TEAEs side by side to the TEAE/TEDRE and a comparison of all TESAEs side by side to the

TESAE/TESDREs will be produced, sorting by system organ class, preferred term, and worst grade.

A listing of fatal AEs and fatal DREs will be provided. **A listing of SAEs and SAE for EOs will be provided.** Listing of SAEs from consent and before first dose of study therapy will also be provided separately.

A listing of treatment-related AEs reported in long term follow-up will be provided for the final CSR and may be analyzed earlier as part of a program-wide analysis.

Potential or known unintended exposure to Talimogene Laherparepvec, related suspected signs or symptoms, and detection of Talimogene Laherparepvec DNA in swabs of suspected herpetic-like lesions in a subject's household member, caregiver, or healthcare provider will be reported in the final CSR. Individual reported cases with available qPCR testing results will be reviewed. Additionally, unintended exposures will be analyzed periodically as part of a program-wide analysis.

10.6.2 Laboratory Test Results

Shifts in grades of safety laboratory values between the baseline and the worst on-study value will be tabulated. Subject incidence of potential hepatotoxicity as identified by the Hy's Law criteria (FDA guidance for Industry Drug Induced Liver Injury: pre-marketing evaluation, July 2009) as well as confirmed DILI events as reported by investigators will be presented.

10.6.3 Vital Signs

Analysis of vital signs will not be performed as routine monitoring and collection of vital sign data is not sufficient to require an analysis.

10.6.4 Electrocardiogram (ECG)

The ECG measurements from this clinical study will be performed as per standard of care for routine safety monitoring. Summaries and statistical analyses of ECG measurements are not planned.

10.6.5 Antibody Formation

The incidence and percentage of subjects who develop anti-pembrolizumab antibodies (binding and if positive, neutralizing) at any time and at last post baseline assessment will be analyzed by Merck.

10.6.6 Exposure to Investigational Product

Summary statistics for exposure to talimogene laherparepvec, including total doses administered, total volume administered, distribution of the number of administrations

with a total volume > 4 mL, duration from the first to the last administration of talimogene laherparepvec, and the average volume received by subject per visit will be provided and will be separated by the first (concentration of 10^6 PFU/ml) and subsequent doses (concentration of 10^8 PFU/ml). Subject incidence and reasons for IP dose change/withheld will be tabulated.

Exposure to pembrolizumab including total doses (in mg) administered, relative dose intensity, duration from the first to the last administration, and the average dose received by subject per visit will be provided. Subject incidence rate and reasons for IP delay, dose change/withheld dose delay, and dose interruption of pembrolizumab will be examined.

A listing of the unique manufacturing lot numbers, and a listing of the subjects administered each manufacturing lot number will be provided.

10.6.7 Exposure to Concomitant Medication

The number and proportion of subjects receiving therapies of interest will be summarized by preferred term or category for each treatment group as coded by the World Health Organization Drug (WHO DRUG) dictionary.

10.6.8 Talimogene Laherparepvec DNA

10.6.8.1 Incidence of Detection of Talimogene Laherparepvec DNA in Lesions Suspected to be Herpetic in Origin

Phase 1b

The number and proportion of subjects with positive qPCR for talimogene laherparepvec DNA detection in any swab of a lesion suspected to be herpetic in origin will be calculated based on the qPCR Suspicious Lesion Swab Analysis Set. An exact 95% CI for the binomial proportion will be calculated ([Clopper & Pearson, 1934](#)).

Individual subjects having a positive qPCR results for talimogene laherparepvec DNA detection will be reviewed.

10.6.8.2 Incidence of Clearance of Talimogene Laherparepvec DNA From Blood and Urine

Phase 1b

The number and proportion of subjects with undetectable talimogene laherparepvec DNA per qPCR among subjects with sample collected in each cycle will be presented. Incidence of clearance of talimogene laherparepvec DNA from Cycle 1, 2, 3, and 4 will

be calculated by cycle. An exact 95% CI for the binomial proportion will be calculated ([Clopper & Pearson, 1934](#)).

Analysis of incidence of clearance of talimogene laherparepvec DNA from blood and urine will be analyzed using the qPCR Blood Clearance Analysis Set and qPCR Urine Clearance Analysis Set, respectively.

10.6.8.3 Rate of Detection and Subject Incidence of Talimogene laherparepvec DNA and Virus From Blood, Urine, Exterior of Occlusive Dressing, Surface of Injected Lesions, and Oral Mucosa

Phase 1b

Rate of detection and subject incidence of talimogene laherparepvec DNA and virus will be analyzed separately for blood, urine, exterior of occlusive dressing, surface of injected lesions, and oral mucosa using qPCR Blood Analysis Set, qPCR Urine Analysis Set, qPCR Exterior Occlusive Dressing Analysis Set, qPCR Injected Lesion Analysis Set, and qPCR Oral Mucosa Analysis Set, respectively.

The number and proportion of subjects who have at least 1 positive qPCR result will be presented. The number and proportion of subjects exhibiting detectable virus from TCID50 assay will also be presented. Numeric results of positive qPCR, and separately for detectable virus from TCID50, will be summarized as a continuous variable. An exact 95% CI for the binomial proportion will be calculated ([Clopper & Pearson, 1934](#)).

Subject incidence and rate of subsequent positive TCID50 testing for positive qPCR testing results will be presented using qPCR Exterior Occlusive Dressing Analysis Set, qPCR Injected Lesion Analysis Set, and qPCR Oral Mucosa Analysis Set.

qPCR and TCID50 results for subjects having a positive qPCR testing will be reviewed.

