Week	Study Treatment ^a													Follow-up Period
	0	0	0	1	2	3	3	3	4	5	6	7	9	Safety Follow-up
Talimogene Laherparepvec Cycle	1	1	1	1	1	2	2	2	2	2	3	3	4	Day 30 Safety Follow-up Visit
Day	1	2	3	8	15	1	2	3	8	15	1	8	1	30 (+ 7) days after end of treatment
Blood ^a	X	X	X	X	X	X	X	X	X	X	X	X	X	X
Urine ^a	X	X	X	X	X	X	X	X	X	X	X	X	X	X
Swab of Surface of Exterior of Occlusive Dressing ^b		X	X	X	(X)	(X)	X	X	X	(X)	(X)	X	(X)	(X)
Swab of Surface of Injected Lesion ^b		X	X	X	X	X	X	X	X	X	X	X	X	X
Swab of Oral Mucosa ^c	X	X	X	X	X	X	X	X	X	X	X	X	X	X

^a Blood and urine sample for real-time polymerase chain reaction (qPCR) testing of talimogene laherparepvec DNA will be performed at the following time points: Cycle 1: day 1 (prior to and approximately 1 hour [\pm 15 minutes], 4 hours [\pm 30 minutes], after talimogene laherparepvec administration), day 2 (24 [\pm 4] hours after talimogene laherparepvec administration), day 3 (48 [\pm 4] hours after talimogene laherparepvec administration), day 8 (\pm 2 days), and day 15 (\pm 2 days). Cycle 2: day 1 (prior to and approximately 1 hour [\pm 15 minutes], 4 hours [\pm 30 minutes], after talimogene laherparepvec administration), day 2 (24 [\pm 4] hours after talimogene laherparepvec administration), day 3 (48 [\pm 4] hours after talimogene laherparepvec administration), and day 8 (\pm 2 days), and day 15 (\pm 2 days). Cycle 3: day 1 (prior to talimogene laherparepvec administration) and day 8 (\pm 2 days). Cycle 4: day 1 (prior to talimogene laherparepvec administration). Blood and urine samples for qPCR testing will also be collected at the 30-day safety follow-up visit (+7 days). Please refer to the Central Laboratory Manual for instructions regarding sample collection, storage, and shipment procedures.

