4.1.3 Exploratory Endpoints

- Phase 1b
 - ORR, CRR, BOR, DCR, and DOR (response evaluation by investigator using modified RECIST v1.1)
 - Incidence of clearance of talimogene laherparepvec DNA from blood and urine
 - Rate of detection and subject incidence of talimogene laherparepvec DNA and virus from blood, urine, exterior of occlusive dressing, surface of injected lesions, and oral mucosa
 - Response rates in injected and uninjected lesions: evaluable lesion incidence of a $\geq 30\%$ decrease in lesion length for ≥ 4 weeks
 - Incidence of detection of talimogene laherparepvec DNA in lesions suspected to be herpetic in origin
 - Potential biomarkers which predict and/or are correlated with clinical outcomes to talimogene laherparepvec and pembrolizumab

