7.5 Biomarker Analysis Set

A Biomarker Analysis Set will be defined separately for each individual candidate biomarker. For exploratory and predictive analyses, the analysis set will include all treated (phase 1b) subjects with a baseline biomarker result and, for analyses of biomarker changes, the analysis set will include all treated (phase 1b) subjects that have a baseline and at least one subsequent biomarker result.

7.6 qPCR Suspicious Lesion Swab Analysis Set

The qPCR Suspicious Lesion Swab Analysis Set will include subjects who are enrolled (phase 1b), receive at least one dose of talimogene laherparepvec / placebo, and have at least one swab sample evaluable result from lesions suspicious to be herpetic in origin during the study. Evaluable samples are sample with either positive, BQL, or not detected results.

7.7 qPCR Blood Analysis Set

The qPCR Blood Analysis Set applies only to the phase 1b and will include treated subjects that have at least one post-dose blood sample evaluable result for qPCR testing of talimogene laherparepvec DNA.

7.8 qPCR Urine Analysis Set

The qPCR Urine Analysis Set applies only to the phase 1b and will include treated subjects that have at least one post-dose urine sample evaluable result for qPCR testing of talimogene laherparepvec DNA.

7.9 qPCR Exterior Occlusive Dressing Analysis Set

The qPCR Exterior Occlusive Dressing Analysis Set applies only to the phase 1b and will include treated subjects that have at least one post-dose exterior occlusive dressing surface swab evaluable result for qPCR testing of talimogene laherparepvec DNA.

7.10 qPCR Injected Lesion Analysis Set

The qPCR Injected Lesion Analysis Set applies only to the phase 1b and will include treated subjects that have at least one post-dose swab of an injected lesion with an evaluable result for qPCR testing of talimogene laherparepvec DNA.

7.11 qPCR Oral Mucosa Analysis Set

The qPCR Oral Mucosa Analysis Set applies only to the phase 1b and will include treated subjects that have at least one post-dose swab of oral mucosa with an evaluable result for qPCR testing of talimogene laherparepvec DNA.

7.12 qPCR Blood Clearance Analysis Set

The qPCR Blood Clearance Analysis Set applies only to the phase 1b and will include treated subjects that have at least one qPCR positive talimogene laherparepvec DNA blood sample, and at least one evaluable subsequent sample at any time during the same cycle.

7.13 qPCR Urine Clearance Analysis Set

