The qPCR Urine Clearance Analysis Set applies only to the phase 1b and will include treated subjects that have at least one qPCR positive talimogene laherparepvec DNA urine sample, and at least one evaluable subsequent sample at any time during the same cycle.

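### The SAP plans DNA clearance rates for cycles 1 to 4, but the sampling schedule cannot support one for cycle 4, or for cycle 3 after its own injection

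*SAP*

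**What the plan says.** SAP 4.1.3 lists "Incidence of clearance of talimogene laherparepvec DNA from blood and urine" as a phase 1b exploratory endpoint. SAP 10.6.8.2 gives the analysis. It reports the number and proportion of subjects with undetectable DNA "among subjects with sample collected in each cycle", and then "Incidence of clearance of talimogene laherparepvec DNA from Cycle 1, 2, 3, and 4", each by cycle and with an exact binomial 95% interval. The analyses use the Blood Clearance and Urine Clearance Analysis Sets.

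Those sets are defined in SAP 7.12 and 7.13. The urine set takes treated subjects with "at least one qPCR positive talimogene laherparepvec DNA urine sample, and at least one evaluable subsequent sample at any time during the same cycle"; the blood set is worded the same way.

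Sampling times are in Protocol Table 6, footnote a. Cycles 1 and 2 each have a pre-dose sample, samples at about 1 and 4 hours, and samples on days 2, 3, 8 and 15. The later cycles are sparse: "Cycle 3: day 1 (prior to talimogene laherparepvec administration) and day 8", and then "Cycle 4: day 1 (prior to talimogene laherparepvec administration" with nothing further in that cycle. The only later sample is at the 30-day safety visit, which Table 6 places under follow-up and not under a cycle.

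**The concern.** A clearance rate needs a subject who was shown to be positive and was then sampled again. The SAP writes that requirement into its analysis sets and ties both samples to one cycle. The schedule takes one sample in cycle 4, before the injection. In cycle 3 it takes two, and the first of these precedes the injection. The plan therefore promises four rates of one kind where the schedule supports two.

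The SAP also does not say whether the set is applied afresh in each cycle or once per subject. Two programmers could produce different tables, one with an empty cycle 4 row and one with a percentage in it. Under Protocol Table 5, footnote n, the first dose is 10^6 PFU/mL and later doses are 10^8 PFU/mL, so readers will be inclined to compare the rows of a by-cycle table. The cycle 3 and 4 rows would not measure the same thing as rows 1 and 2.

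**Working it through.** The documents state no figure to reproduce here, so the check is a count from the schedule.

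**Inputs.** Sampling times come from Protocol Table 6, footnote a. The same-cycle rule comes from SAP 7.12 and 7.13. The three-week dosing interval comes from Protocol Table 5, footnote n, and puts doses 1 to 4 nominally on study days 1, 22, 43 and 64.

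**Same-cycle pairs.** With n samples in a cycle, the number of pairs of one sample and a later one is n(n − 1)/2. Using post-dose samples only gives the pairs that begin after that cycle's injection.

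| | Cycle 1 | Cycle 2 | Cycle 3 | Cycle 4 |
|---|---|---|---|---|
| Scheduled samples | 7 | 7 | 2 | 1 |
| Of these, post-dose | 6 | 6 | 1 | 0 |
| All same-cycle pairs | 7×6/2 = 21 | 21 | 2×1/2 = 1 | 1×0/2 = 0 |
| Pairs beginning post-dose | 6×5/2 = 15 | 15 | 1×0/2 = 0 | 0 |

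The single cycle 3 pair runs from the pre-dose sample to day 8. A positive on day 8 has no later cycle 3 sample to complete a pair.

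**Nominal days from the most recent injection to the last scheduled in-cycle sample.**

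- Cycle 1: day 15, so 15 − 1 = 14 days after dose 1.
- Cycle 2: day 15, so 14 days after dose 2.
- Cycle 3: day 8, so 8 − 1 = 7 days after dose 3.
- Cycle 4: pre-dose on study day 64, so 64 − 43 = 21 days after dose 3, before dose 4 is given.

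**What is reported under each reading.**

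- *Set applied per cycle.* Cycle 4 has no scheduled qualifying pair, so its denominator is zero and no interval can be calculated. Cycle 3 admits only subjects still positive before dose 3, and judges them on day 8, after a new injection.
- *Set applied once per subject, with the cycle denominator in SAP 10.6.8.2.* A subject who qualified in cycle 1 or 2 can be counted in later cycles. Cycle 4 is then the share undetectable before dose 4. Cycle 3 is non-detection on day 8 without a documented positive after dose 3.

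**Schedule after the proposed change.** Take each cycle's post-dose samples and add the next cycle's pre-dose sample as the closing one. Cycles 1 and 2 then have 6 + 1 = 7 samples and 21 pairs each. Cycle 3 has 1 + 1 = 2 samples and 1 pair. Cycle 4 has no post-dose in-cycle sample to enter on. The closing times are 22 − 1, 43 − 22 and 64 − 43, which is 21 days in each of cycles 1 to 3.

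**The case against.** The strongest reply is that SAP 7.12 and 7.13 read most naturally as a one-time, subject-level entry rule, with the by-cycle denominator supplied separately in SAP 10.6.8.2. A percentage can then be calculated in all four cycles. A subject with an earlier positive who is undetectable 21 days after dose 3 has, in a plain sense, cleared the DNA. The SAP never promises clearance per dose and plans no comparison between cycles. SAP 10.6.8.3 separately reports detection, so a day 8 positive in cycle 3 is not lost. Pair counts also overstate what matters, since one pair is enough for entry. In cycle 1, the 21 − 15 = 6 pairs that start before any study injection are not realistic routes in, because prior treatment with the product is excluded (Protocol 4.2, criterion 208).

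Part of this stands. The zero denominator arises on only one reading, the pair counts describe the schedule and not the number of subjects affected, and nothing primary is touched. It does not rescue the cycle 3 and 4 figures. On the subject-level reading, the cycle 4 row reports status before dose 4 under the name of cycle 4 clearance. SAP 10.6.8.3 gives detection, which is a different quantity. The 30-day sample cannot complete a pair either: no rule assigns it to a cycle, and 30 (+7) days after the end of treatment lies outside a nominal three-week cycle. The contents of the SAP appendices were not available to check, but SAP 10.6.8.2 does not refer to any of them.

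**Conclusion.** The concern holds. Followed as written, the plan gives a cycle 4 figure that is either empty or a pre-dose status under the wrong name. The cycle 3 figure is not comparable with cycles 1 and 2. The number of qualifying pairs that begin after the injection is 15, 15, 0 and 0, so within-cycle clearance following an injection can be estimated for cycles 1 and 2 only.

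This rests on scheduled samples and nominal times. Protocol 7.2.3 and 6.2.1.2 let dose intervals vary, so no range of gaps is given. The documents do not report positivity by time point, so the number of subjects affected is unknown. The consequence is minor: the endpoint is exploratory and descriptive, cycles 1 and 2 are well sampled, and no primary, secondary or go/no-go result depends on it. It is still worth correcting, because the table would otherwise mislead.

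**What to change.** Amend SAP 7.12, 7.13 and 10.6.8.2 as follows.

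- A subject enters a cycle's analysis on a positive sample taken after that cycle's injection. The subjects so entered form that cycle's denominator.
- The day 1 pre-dose sample of the next cycle counts as the closing sample of the preceding one.
- Report clearance for cycles 1 and 2. Report cycle 3 only as day 8 positives judged at the cycle 4 pre-dose sample, and label it that way. Give no cycle 4 clearance figure.
- Report the 30-day follow-up sample separately, as detection at follow-up, with the time since the last injection.

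A simpler alternative is to restrict by-cycle clearance to cycles 1 and 2 and to present the cycle 3 and 4 pre-dose results as residual detection.

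Two clarifications could be made at the same time, although the point does not depend on them. One is whether any later sample or the last sample must be undetectable. The other is how a BQL result counts, since SAP 7.6 lists it apart from non-detection: "Evaluable samples are sample with either positive, BQL, or not detected results".

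The cost is SAP wording and some reprogramming, with no new samples. SAP 11 shows that the phase 1b primary analysis had already been reviewed, so the change should be labelled post hoc if these samples have been analysed.

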10.7 Pharmacokinetic or Pharmacokinetic/Pharmacodynamic Analysis

Pembrolizumab PK sample and data analysis will be provided by Merck.

Pembrolizumab concentrations and pharmacokinetic (PK) parameters including the C_{min} , C_{max} , and AUC will be listed and summarized using descriptive statistics. Preliminary analysis will include examining the PK parameters for extreme values falling out of the standardized ranges of deviations as predicted by the existing population PK model. The impact of any outliers on the results of the analyses will be evaluated. Population PK analysis, based on pharmacokinetic PK data obtained in this study together with that obtained from other studies, will be conducted.

The analysis plan and report from that population PK analysis will be described in separate documents.

11. Changes From Protocol-specified Analyses

Following the review of the phase 1b primary analysis of efficacy and safety, a decision was made by the sponsor to not proceed with the phase 3 portion of this study.

Therefore, all study design and statistical methods related to the phase 3 that are described in the protocol are not included in this SAP. None of the phase 3 analyses specified in the protocol will be performed.

12. Literature Citations / References

Center for Drug Evaluation and Research, Center for Biologics Evaluation and Research, Food and Drug Administration. Guidance for industry. Drug-induced liver injury: premarketing clinical evaluation. Drug Safety. July 2009.

Clopper, C. and Pearson, E. (1934) The Use of Confidence or Fiducial Limits Illustrated in the Case of the Binomial. *Biometrika*, **26**, 404–413

Council for International Organizations of Medical Sciences (CIOMS) Working Group VI. CIOMS; Geneva, Switzerland: 2005. Management of safety information from clinical trials.

Eisenhauer, A., et al. (2009) New Response Evaluation in Solid Tumors: Revised RECIST Guideline (version 1.1). *EJC*, **45**, 228-247.

13. Appendices
